12.5. Injection Site Assessment

The injection site and surrounding area will be assessed by the investigator at 1 min and 15 min post-dose on Day 1 and at the EOS visit. Reactions to the study drug injection will be documented using a numerical scoring system.

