6. INVESTIGATIONAL PLAN

6.1. Description of Overall Study Design and Plan

The NKF-INS(A) clinical program is designed to demonstrate biosimilarity to the US and EU-insulin aspart (EU-NovoRapid[®], and US-NovoLog[®]) by comparing the PK and PD of NKF-INS(A) to the reference products after a single SC dose.

Study NKF-INS(A)-101 is a Phase 1, 12-hour euglycemic glucose clamp study conducted using a randomized, double-blind, three-period, three-treatment, six-sequence, crossover design. The study will compare single doses of the proposed insulin biosimilar (NKF-INS(A)) with respective EU- and US-reference products in healthy male participants.

Written informed consent will be obtained from all participants, and the study will be conducted in accordance with the principles of Good Clinical Practice (GCP) as defined by the International Conference of Harmonization (ICH).

The study will consist of:

- a screening period of up to 4 weeks (Days -28 to -1),
- three treatment periods each consisting of 1-day dose administrations and euglycemic clamp periods (periods 1, 2, and 3) separated by a washout period of 3-14 calendar days between treatment periods 1 and 2, and a washout period of 5-21 calendar days between treatment periods 2 and 3, and
- a follow-up period of 2-11 days after last dose.

The entire study duration will be a maximum of 11 weeks.

Three insulin products (NKF-INS(A), EU-NovoRapid[®], and US-NovoLog[®]) will be administered over three treatment periods. Upon admission to the clinical research unit (CRU) on Day -1, participants will be randomized to one of six treatment sequences in a 1:1:1:1:1:1 ratio, receiving a single SC dose of 0.3 U/kg administration of one of the three study drugs on each dosing day.

A 12-hour euglycemic glucose clamp will be conducted using a manual clamp technique, which will monitor the subject's blood glucose and administer glucose infusion rate (GIR) to maintain blood glucose close to the target blood glucose concentration. The clamp procedure will be initiated, maintained, and terminated, in accordance with the site standard operating procedures (SOPs). The participant's blood glucose will be maintained within a pre-defined target window per site SOP and clinical judgment for the participant by manually adjusting the GIR.

Blood samples will be collected at pre-specified intervals before and up to 12 hours after dosing for measurement of blood glucose, serum insulin, and C-peptide.

[figure not shown]

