6.3. End of Study

A participant will have fulfilled the requirements for study completion if/when the participant has completed all three treatment periods and the end of study (EOS) visit within 2-11 days after last administration of the study drug.

The EOS is defined as the date of the last visit for the last participant in the study/last scheduled procedure shown in the schedule of assessments ([Table 3](#)).

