9. STUDY PROCEDURES

Assessments and their timing to be performed are outlined in the schedule of assessments ([Table 3](#)).

See Sections [10](#), [11](#), [12](#), and [13](#) for additional details regarding PK, PD, safety, and other assessments, respectively.

The Investigator may, at his or her discretion, arrange for a participant to have an unscheduled assessment, especially in the case of AEs that require follow up or are considered by the Investigator to be possibly related to the use of study treatment. The unscheduled visit page in the eCRF must be completed for all unscheduled assessments.

Table 3. Schedule of Assessments

Assessment	Screening	Euglycemic Clamp Procedure Treatment Periods 1-3 ¹			EOS Visit Within 2-11 Days After Last Administration of Study Drug
	-28 to -1 Days Prior to Treatment Period 1	Day -1	Clamp Procedure Starting the Morning of Day 1 for 12 Hours ²	Post- Clamp (Day 2)	
Informed consent	X				
Demographic data ³	X				
Alcohol and tobacco consumption patterns	X				
Medical and medications history ⁴	X	X			
Inclusion/exclusion criteria	X	X			
Admission to CRU ⁵		X			
Randomization			X ⁶		
Discharge from CRU				X	
Height/weight ⁷	X	X			
Physical examination ⁸	X				X
Vital signs ⁹	X		X	X	X
12-lead ECG	X				X
Hematology ¹⁰	X				X
Clinical chemistry ¹¹	X				X
Blood coagulation ¹²	X				
Serology tests (HBsAg, IgM anti-HBc, HCV, ¹³ HIV)	X				
Urinalysis ¹⁴	X				
Urine screen for drugs of abuse ¹⁵	X	X			
Alcohol breath test ¹⁶	X	X			
Human insulin antibodies	X				
Oral glucose tolerance test ¹⁷	X				
Study drug administration ¹⁸			Day 1 at time = 0 hours/0 min		
Injection site assessment ¹⁹			X		X
GIR			X		
Adverse events					→

Assessment	Screening	Euglycemic Clamp Procedure Treatment Periods 1-3 ¹			EOS Visit Within 2-11 Days After Last Administration of Study Drug	
	-28 to -1 Days Prior to Treatment Period 1	Day -1	Clamp Procedure Starting the Morning of Day 1 for 12 Hours ²	Post-Clamp (Day 2)		
Concomitant medications				→		
PK, PD, C-peptide, and glucose sampling (see Table 4)						

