18 From 1 hour before study drug administration until 3 hours post-dose, the injection site will be kept at a constant temperature. The time of injection is defined as time zero (0 hour/0 min) and marks the start of the clamp period, which will continue for up to 12 hours or until the GIR is 0 and blood glucose remains stable.

19 The injection site will be assessed at 1 min and 15 min post-dose on Day 1 and at the EOS visit. Reactions to the study drug injection will be documented using a numerical scoring system.

Table 4. Pharmacokinetic, Pharmacodynamic, C-Peptide, and Glucose Sampling Schedule

Sample	Pre-dose (minutes)		Post-dose (minutes)																		
	60	30	0	5	10	20	30	40	50	60	75	90	105	120	135	150	180	210	240	300	600
Insulin (serum)	X	X	X	X	X	X	X	X	X	X	X	X	X	X	X	X	X	X	X	X	X
C-peptide (serum)	X	X	X	X	X	X	X	X	X	X	X	X	X	X	X	X	X	X	X	X	X
Blood glucose			Every 3 minutes											Every 5 minutes				Every 10 minutes			

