12.6.2.2. Parameters for Adverse Events Collection

All nonserious AEs and SAEs will be recorded on the AE eCRF. SAEs will also be immediately reported to the Sponsor safety representative in accordance with Section [12.5.5](#).

Nonserious and SAEs will be documented in the clinical database with the highest severity documented during the duration of each serious or nonserious episode. Each AE is to be documented in the eCRF with reference to date of onset, severity, relationship to study drug, treatment of event, and outcome.

All AEs are to be followed up until resolution or a stable clinical endpoint is reached, as determined by the Investigator. Changes in AEs and resolution dates are to be documented in the eCRF.

Participants will be instructed by the Investigator to report AEs at each study visit. All volunteered, elicited, and observed AEs are to be recorded. A consistent methodology of nondirective questioning should be adopted for eliciting AE information at all participant evaluation timepoints. Examples of nondirective questions include the following:

- “How are you feeling?”
- “How have you felt since your last clinic visit?”

- “Have you had any new or changed health problems since you were last here?”
- “Have you taken any new medications since your last visit?”

The following considerations should also be made regarding AE and SAE reporting:

- All medical and psychiatric conditions present at screening (i.e., conditions present before the AE reporting period) will be considered preexisting conditions and documented in the medical history eCRF. A preexisting condition is not to be reported as an AE. If a preexisting condition worsens during the study treatment period, the event should be reported as an AE. Planned hospitalization for a preexisting condition, or a procedure required by the protocol, without serious deterioration in health, is not considered an SAE.
- Diagnostic and therapeutic noninvasive and invasive procedures, such as surgery, should not be reported as AEs. A medical condition for which an unscheduled procedure was performed, should however be reported if it meets the definition of an AE. For example, an acute appendicitis, and not the appendectomy, should be reported as the AE.

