14.5. Safety Analysis

All analyses of safety will be conducted on the Safety Population unless otherwise specified in the SAP.

All reported AEs will be graded using NCI CTCAE version 5.0 and will be coded using the Medical Dictionary for Regulatory Activities, version 26.0. The incidence of treatment-emergent AEs (TEAEs) will be included in incidence tables. Events with missing onset dates will be included as treatment-emergent. If a participant experiences more than 1 occurrence of the same AE, the occurrence with the greatest severity and the closest association with the study treatment will be used in the summary tables. All TEAEs will be summarized by treatment group (NKF-INS(A), US-NovoLog®, and EU-NovoRapid®) as follows:

- All AEs
- Grade ≥ 3 AEs
- AEs related to study treatment, including related Grade ≥ 3 AEs
- All adverse reactions
- SAEs

All AEs will be listed by participant, along with information regarding onset, duration, relationship and severity to study treatment, action taken with study treatment, treatment of event, and outcome.

Clinical laboratory data (hematology, clinical chemistry [including glucose], coagulation, and urinalysis) and vital signs (heart rate, respiratory rate, systolic and diastolic blood pressure, and temporal or ear temperature measurements) will be summarized by treatment group and

scheduled visits using descriptive statistics, including mean values and mean change from screening values, as well as numbers of participants with values outside limits of the normal range at each timepoint. Shift tables will be provided presenting change from screening values to the last EOS visit.

The frequency of ECG abnormalities (e.g., heart rate, PR interval, QRS complex, and QT-interval corrected by Fridericia's formula [Fridericia's corrected QT]) will be summarized by treatment group and scheduled visits using counts and percentages.

Participant ECG status (normal, abnormal clinically significant, or abnormal not clinically significant) may be summarized for each scheduled ECG and shifts from screening may be tabulated.

Injection site reactions will be summarized by treatment group and scheduled visits. The number and percentage of participants having reactions at each assessment timepoint, overall and by specific reaction subtype, will be presented.

Summary tables will be provided for concomitant medications initiated during the study period.

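### In participants who complete the study, no scheduled injection-site score after 15 minutes is tied to the Period 1 or Period 2 product

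*Protocol*

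**What the plan says.** Protocol 12.5 schedules three looks at the site: it "will be assessed by the investigator at 1 min and 15 min post-dose on Day 1 and at the EOS visit". Footnote 19 of Table 3 repeats this ("The injection site will be assessed at 1 min and 15 min post-dose on Day 1 and at the EOS visit"), and SAP 21.3 gives the same times. The instrument is numerical: "Reactions to the study drug injection will be documented using a numerical scoring system". The scale itself is not given.

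In Table 3 the injection-site row is marked in the clamp column, which covers Treatment Periods 1-3, and in the EOS column. It is not marked at Post-Clamp Day 2 or on Day -1. The EOS column is headed "EOS Visit Within 2-11 Days After Last Administration of Study Drug", and Protocol 6.3 defines a completer as someone who has "completed all three treatment periods and the end of study (EOS) visit within 2-11 days after last administration of the study drug". Treatment periods are "separated by a washout period of 3-14 calendar days between treatment periods 1 and 2, and a washout period of 5-21 calendar days" between Periods 2 and 3 (Protocol 6.1).

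On reporting, Protocol 14.5 says "Injection site reactions will be summarized by treatment group and scheduled visits", with counts and percentages at each timepoint. SAP 21 opens by saying that its assessments will appear in listings only. SAP 21.3 nevertheless plans a summary by kind of assessment and time, and does not mention treatment.

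**The concern.** Injection site reactions are named among the secondary safety endpoints, and this is the first clinical study of the test product. A score at 1 and 15 minutes can show an immediate reaction. Redness, swelling or induration that develops over hours would need a later look, and the plan schedules only one, at EOS after the last period.

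Participants are still in the unit on Day 2 of every period, when vital signs are taken, but the site is not on the list for that visit. For products given in Periods 1 and 2, the next late score comes after one or two further injections in the same perumbilical area.

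The EOS row of the table planned in Protocol 14.5 also has no stated rule for which product a score belongs to. At stake is whether a difference in delayed local tolerability between test and reference could be seen in the scored data.

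**Working it through.** **1. Reproduce the visit days.** SAP Table 6.1 puts the post-study visit on Day 16-52. Starting from the Period 1 post-clamp day (Day 2):

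- Period 2 admission: 2 + 3 to 2 + 14 = Day 5-16; dose Day 6-17; post-clamp Day 7-18.
- Period 3 admission: 7 + 5 to 18 + 21 = Day 12-39; dose Day 13-40; post-clamp Day 14-41.
- EOS: 14 + 2 to 41 + 11 = Day 16-52, as stated.

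The SAP therefore counts the 2-11 days from the post-clamp day. Counted from the last dose, as the protocol words it, EOS is Day 15-51. The one-day difference does not affect this point.

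**2. Time from each dose to the late score in a completer** (EOS 2-11 days after the last dose). Dose-to-dose gaps under the SAP convention are 5-16 days (Period 1 to 2) and 7-23 days (Period 2 to 3).

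| Product given in | SAP day convention | Washout read as dose-to-dose |
|---|---|---|
| Period 3 | 2-11 days | 2-11 days |
| Period 2 | 7 + 2 to 23 + 11 = 9-34 days | 5 + 2 to 21 + 11 = 7-32 days |
| Period 1 | 5 + 7 + 2 to 16 + 23 + 11 = 14-50 days | 3 + 5 + 2 to 14 + 21 + 11 = 10-46 days |

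**3. Coverage by product.** There are six sequences in equal ratio, and each product is last in 2 of 6.

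| | 54 completers | 36 completers, still balanced |
|---|---|---|
| Administrations | 3 × 54 = 162 | 3 × 36 = 108 |
| Followed directly by EOS | 54 | 36 |
| No late score of their own | 108 (67%) | 72 (67%) |
| Per product: with a late score | 54 × 2/6 = 18 | 36 × 2/6 = 12 |
| Per product: without | 54 − 18 = 36 | 36 − 12 = 24 |

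Each completer has one EOS visit, following one product. No completer has a late score for two products, so the late comparison is between groups of 18 (or 12) different participants and the crossover gives it no within-subject contrast.

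**4. What the smaller count means.** If no late reaction is scored among m exposures, the exact one-sided 95% upper limit on the rate is 1 − 0.05^(1/m): 15.3% for m = 18 against 5.4% for m = 54, and 22.1% for m = 12 against 8.0% for m = 36.

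The documents give no late-reaction rate. For an assumed rate p of reactions visible when scored, the chance of scoring at least one for a product is 1 − (1 − p)^m:

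| Assumed p | m = 18 | m = 54 | m = 12 | m = 36 |
|---|---|---|---|---|
| 2% | 30% | 66% | 22% | 52% |
| 5% | 60% | 94% | 46% | 84% |
| 10% | 85% | >99% | 72% | 98% |

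The columns m = 54 and m = 36 are what a late score in every period would give.

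**5. Product assignment and reporting.** SAP 18.2.3 assigns an adverse event to the last product received before onset. No matching rule exists for site scores. Protocol 14.5 promises results by treatment and visit, while SAP 21.3 names no treatment. Under SAP Section 8, tables default to randomized sequence unless otherwise specified. Protocol Section 14 lets the SAP prevail where the two differ, so the product-level table may not be produced at all.

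**The case against.** The strongest answer is that the endpoint is worded as adverse event assessments that include injection site reactions, so adverse event capture is its own proper route. That route is open throughout. Events are collected from first dose to EOS, graded, and attributed to the last product given. It is true that "A consistent methodology of nondirective questioning should be adopted for eliciting AE information", but the same section requires volunteered, elicited and observed events alike to be recorded, so a reaction that staff notice must be entered. Participants stay in the unit until Day 2, and the site is kept at constant temperature until 3 hours after dosing. Symptom-driven examinations and unscheduled assessments are allowed at the Investigator's discretion. Participants who withdraw early are asked to complete the EOS assessments then, so a product given in Period 1 or 2 can receive a late score that way.

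All of this stands, and it rules out two stronger readings. A reader might infer that delayed reactions to the first two products are never captured; the documents do not support that. A reader might also infer that the EOS check covers only the Period 3 site. No text limits it so: the assessment covers the site and its surroundings, and every dose goes into the same perumbilical area. The documents are silent on which site and product an EOS score refers to.

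Nor do the documents give a frequency or time course for delayed reactions, so no number of missed events can be claimed. Amendment 1 added the EOS check and clarified Section 12.5 on regulatory recommendation, so the schedule has had some scrutiny. None of these routes, however, is a scheduled score after 15 minutes tied to the product given in Period 1 or 2.

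**Conclusion.** The point holds for the scheduled numerical scoring of participants who complete the study. Two thirds of each product's exposures have no score after 15 minutes belonging to their own period, and the remaining third are scored at a delay anywhere between 2 and 11 days. The count assumes equal sequences and no dropout; the 67% is unchanged with 36 completers if balance is kept.

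Delayed reactions in Periods 1 and 2 are unscored, not necessarily missed. The effect is confined to a descriptive secondary safety summary and does not reach the PK/PD conclusions. This is a worthwhile and cheap improvement to the schedule, together with a real need to reconcile how the protocol and SAP report these scores.

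**What to change.** - In Table 3, Protocol 12.5 and SAP 21.3, add the same numerical injection-site score at the existing Post-Clamp (Day 2) visit of every period, before discharge, and assign it to that period's product. Every completer then has a late score for all three products, at a similar delay and within subject.
- State that the EOS score refers to the last product received: the Period 3 product for completers, the product of the last period dosed for early withdrawals.
- Reconcile Protocol 14.5 (by treatment and visit) with SAP 21 (listings only) and SAP 21.3 (treatment not named), so that the SAP specifies the product-level table.

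The cost is a schedule and eCRF amendment and a brief visual check in each period. No new visit or invasive procedure is needed. A Day 2 score will not show a reaction that first appears after discharge; in Periods 1 and 2 those would still rely on adverse event reporting.

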12.6. Adverse Events

12.6.1. Definitions

12.6.1.1. Adverse Event

Any untoward medical occurrence in a patient or clinical investigation subject administered an investigational product which does not necessarily have to have a causal relationship with this treatment. An AE can, therefore, be any unfavorable and unintended sign (including an abnormal laboratory finding, for example), symptom, or disease temporally associated with the use of an investigational product, whether or not considered related to the investigational product.

12.6.1.2. Adverse Reaction

A response to a medicine in humans which is noxious and unintended, and which occurs at any dose, and which can also result from overdose, misuse, or abuse of a medicine. Response to a medicinal product in this context means that a causal relationship between the medicinal product and an AE is at least a reasonable possibility.

12.6.1.3. Serious Adverse Event

Any untoward medical occurrence, in the view of either the Investigator or Sponsor, that:

- Results in death
- Is life-threatening
 - An AE is life-threatening if the participant was at immediate risk of death from the event as it occurred (i.e., it does not include a reaction that might have caused death if it had occurred in a more serious form).
- Requires or prolongs inpatient hospitalization
 - A hospitalization is defined as ≥ 24 hours in hospital or an overnight stay. Complications occurring during hospitalization are AEs and SAEs if they cause prolongation of the current hospitalization. Hospitalization for elective treatment of a preexisting, non-worsening condition is not, however, considered an AE. The details of such hospitalizations must be recorded in the medical history/procedures or physical examination page of the eCRF.
- Results in persistent or significant disability/incapacity
 - An AE is incapacitating or disabling if it results in a substantial and/or permanent disruption of the participant's ability to carry out normal life functions.
- Results in a congenital anomaly/birth defect
- Is another medically important event

In addition, medical and scientific judgment is required to decide if prompt notification is required in situations other than those defined for SAEs. This may include any event that the Investigator regards as serious that did not strictly meet the criteria above but may have jeopardized the participant or required intervention to prevent one of the outcomes listed

above, or that would suggest any significant hazard, contraindication, AE, or precaution that may be associated with the use of the study treatment.

Other important medical events that may not be immediately life-threatening or result in death or hospitalization, based upon appropriate medical judgment, are considered SAEs if they are thought to jeopardize the participant and/or require medical or surgical intervention to prevent one of the outcomes defining an SAE. SAEs are critically important for the identification of significant safety problems; therefore, it is important to consider both the Investigator's and the Sponsor's assessment.

12.6.1.4. Pre-treatment Adverse Event

An AE with a start date and time before the first dose of study drug.

12.6.1.5. Treatment-Emergent Adverse Event

An AE with a start date and time on or after the first dose of study drug.

12.6.1.6. Unexpected Adverse Reaction

An adverse reaction in which the nature, specificity, severity, and outcome is not consistent with the referenced safety information.

12.6.2. Adverse Event Collection, Assessment and Reporting

12.6.2.1. Observation Period for Assessment of Adverse Events

For the purposes of this study, the period of observation for collection of AEs (including nonserious AEs and SAEs) extends from the time the participant begins study treatment (Day 1) until the EOS visit (within 2-11 days after last administration of the study drug). If a participant withdraws or is discontinued from the study by the Investigator, AEs should be collected from the time the participant begins study treatment (Day 1) up to the completion of EOS assessments.

